2. PROTOCOL SYNOPSIS

TITLE	Characterization of humoral and cellular immunity for tick-borne encephalitis (TBE) vaccination in allogeneic blood and marrow graft						
	recipients: a pilot study						
OBJECTIVES	Primary Objective						
			moral immunoge	•			
	-		nd marrow graf		•		
			without previou			-	
			ntibody levels us	-		(NT) and	
	enzyme-linked immunosorbent assay test (ELISA)						
	Secondary Ob	-					
			r immunogenici				
	-		recipients, by cytokine levels				
			mononuclear	-			
			l human albumin			annnann	
	-		une status in HS	-	-	and after	
			easured by qua	•	•	-	
			orescence staini		-		
	lymphocyt	es and f	low cytometry ar	nalyses			
DESIGN / PHASE	Prospective, of	pen-labe	el phase II study.				
STUDY PLANNED DURATION	First patient	07/	Last nationt	12/	Last patient	12/	
	First visit	2014	Last patient First visit	2016	Last visit	2017	
CENTER(S)	Single center s	tudy of t	the Medical Univ	ersity of	Vienna in Aust	ria	
/ COUNTRY(IES)	_						
PATIENTS / GROUPS	26 HSCT patie	nts in the	e study group				
	26 healthy vol	unteers	in the control gro	pup			
INCLUSION CRITERIA			years who				
		-	e an allogeneic H			go or	
			eers without pre		E vaccination		
EXCLUSION CRITERIA	Previous TBE vaccination following HSCT						
	• HSCT patients with extremely severe acute graft versus host						
	disease (receiving prednisone >0.5 mg/kg bodyweight as part of a						
	combinati	on the	rapy or a thr	ee age	nt immunosu	ppressive	
	treatment)						
	Previous	TBE viru	s infection, prev	vious de	ngue virus infe	ection or	
	vaccination against yellow fever or Japanese encephalitisAny acute febrile illness in the 2 weeks prior to or at the time of						
	enrolment						
	• A history of severe allergic reactions or anaphylaxis after						
	vaccination						
	If female, are pregnant or lactating						
	 If belonging to the healthy control group, are immunosuppressed Belance of underlying malignant disease 						
STUDY PERIODS	Relapse of underlying malignant disease						
	 The active phase of the study for each participant is 44-56 weeks No additional controls are needed 						
	No addition	iui contr	ois ure needed				

	 The total duration of the study is estimated to be 4 years
STUDY DRUG	TBE vaccine – FSME IMMUN 0.5 ml ($2.4 \mu g$)
COMPARATIVE DRUG	No
EFFICACY ENDPOINTS	Number of subjects with antibody response to TBE vaccination
EFFICACT ENDFOINTS	associated with protection 28 days after the second and third
	vaccination
TOLERABILITY / SAFETY	Number of subjects with systemic reactions after vaccination
PHARMACOKINETIC /	Νο
PHARMACODYNAMIC	
QUALITY OF LIFE /	No
PHARMACOECONOMIC	
ENDPOINTS	
STATISTICAL METHODOLOGY	Primary Endpoint
	To assess humoral immunogenicity of the TBE vaccination in
	allogeneic HSCT recipients compared to healthy volunteers without
	previous TBE vaccination, the outcome of the neutralilzation test (NT)
	will be assessed four weeks after the second vaccination. Therefore,
	the number of subjects with NT titers against TBE virus >10
	(=seroconversion rate), assumed to be the threshold for antibody-
	mediated protection, will be evaluated.
	Null and alternative hypotheses:
	H ₀ : There is no statistical difference in the seroconversion rate between
	the study population and the control group
	H ₁ : There is statistical difference in the seroconverion rate between the
	study population and the control group
	Type-I and -II errors – power:
	Alpha 0.05. Power 0.8.
	Sample size calculation
	The calculation of the sample size was performed using nQuery 6.1. The primary endpoint is the outcome of the NT against 4 weeks after
	the second vaccination (positive test: Yes/No). Because of deviation of the antibody concentrations from normal distribution (NT level <=10 not detectable indicating a negative test), the outcome is reduced to a binary but clinically more relevant outcome (seroconversion rate: NT
	levels >10 indicates a positive test). Previously, in a study with heart transplant recipients a seroconversion rate of 35% was detected compared to 100% in the healthy control group. In our study we expect
	a seroconversion rate of at least 90% in the healthy control group. In the HSCT patients we expect a seroconversion not exceeding 50%. The
	calculation of the sample size was performed using the following assumption: Significance level alpha 0.05, Power 0.8, ratio of HSC1
	patients/healthy volunteers: 1/1. With a total number of 46 participants (23 HSCT patients and 23 healthy volunteers) the assumed
	difference in the seroconversion rate between groups can be detected (using a two-sided Fisher's Exact Test) with 80% Power. We added 10%
	to adjust for potential loss-to-follow-up which results in 26 HSCT patients and 26 healthy volunteers.

Statistical methodology

The primary endpoint (outcome of NT 4 weeks after the second vaccination) will be analysed using Fisher's Exact Test. For the seroconversion rates, 95% confidence intervals will be calculated. The secondary endpoints (NT 4 weeks after the third vaccination, ELISA after the second and third vaccination, cellular immunity, immunoglobulin levels, immune reconstitution and safety data) will be analysed using descriptive statistics.

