8.4 Benefit and risk assessment

After vaccination with the inactivated TBE virus K23, in particular following the administration of the complete primary immunization, it is highly probable that the majority of subjects participating in the phase II clinical study will be protected against TBE, one of the most severe infections of the central nervous system. Allogeneic HSCT recipients, particularly those with chronic GVHD, have a high risk for microbial infections including TBE infection. Therefore, primary vaccination of HSCT recipients is recommended in risk areas one year

after HSCT at the latest independently of previous TBE vaccination before HSCT. The used TBE-vaccine is registered in Austria for more than one decade. Its safety and efficacy have been already demonstrated in many clinical trials. Therefore, unexpected adverse events due to the vaccination are not assumed. However, the following side effects have to be considered:

- very common (>1/10): local reactions at the site of injection, transient redness, and swelling.

- common (>1/100;<1/10): systemic reactions including fever, fatigue, headache, muscular pain, arthralgia. These side-effects usually occur within 72 hours after the vaccination, abate within 1-2 days, but do not acquire any medical treatment. All adverse events will be listed in the study documents and have to evaluated by the investigator for causality to the vaccination. After venous puncture local reactions, a hematoma or phlebitis can occur. However, the planed venous punctures withdraw only minor volumes of blood and do not impair the patient's health.

Therefore, it can be speculated that this study does not exhibit an exceptional risk for the patients.

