8.5.2.6. Visit 5 /1. Evaluation of immune status (Day 84 ± 14 days)

The following activities will be performed in HSCT patients only:

- The investigator will ask all subjects about any adverse experiences occurring since Visit 4. All adverse experiences will be documented in the CRF.
- Blood draw of 10 ml for immune status and quantitative immunoglobulin levels
- Pregnancy test in females capable of bearing children.

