8.5.2.7. Visit 6 /3. Vaccination and evaluation of immune status (Day 270-365)

The following activities will be performed:

- The investigator will ask all subjects about any adverse experiences occurring since Visit 5. All adverse experiences will be documented in the CRF.
- Physical examination including body temperature measured axillary.
- Pregnancy test in females capable of bearing children.
- Third vaccination: for details see Visit 1.
- Post vaccination observation period (30 minutes): for details see Visit 1.
- Blood draw of 10 ml for immune status and quantitative immunoglobulin levels

8.5.2.8. Visit 7 /2. Evaluation of cellular immunity (Day 277-372, 7 ± 2 days after the third vaccination)

The following activities will be performed in HSCT patients only:

- The investigator will ask all subjects about any adverse experiences occurring since Visit 6. All adverse experiences will be documented in the CRF.
- Blood draw of 40 ml for cellular immunity

8.5.2.9. Visit 8 /2. Evaluation of humoral immunity (Day 298-393, 28 ± 7 days after the third vaccination)

The following activities will be performed in HSCT patients only:

- The investigator will ask all subjects about any adverse experiences occurring since Visit 7. All adverse experiences will be documented in the CRF.
- Blood draw of 10 ml for serum antibody determination (NT, ELISA)
- Pregnancy test in females capable of bearing children.

After this visit, the patients will have completed the study.

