9. SAFETY DEFINITIONS AND REPORTING REQUIREMENTS

9.1 Adverse events (AEs)

9.1.1 Summary of known and potential risks of the study drug

The following side effects have to be considered:

- very common (>1/10): local reactions at the site of injection, transient redness, and swelling.

- common (>1/100;<1/10): systemic reactions including fever, fatigue, headache, muscular pain, arthralgia. These side-effects usually occur within 72 hours after the vaccination, abate within 1-2 days, but do not acquire any medical treatment. All adverse events will be listed in the study documents and have to evaluated by the investigator for causality to the vaccination. After venous puncture local reactions, a hematoma or phlebitis can occur. However, the planed venous punctures withdraw only minor volumes of blood and do not impair the patient's health.

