9.1.2 Definition of adverse events

An AE is any untoward adverse change from the subject's baseline condition, i.e., any unfavorable and unintended sign including an abnormal laboratory finding, symptom or disease which is considered to be clinically relevant by the physician that occurs during the course of the study, whether or not considered related to the study drug.

Adverse events include:

- Exacerbation of a pre-existing disease.
- Increase in frequency or intensity of a pre-existing episodic disease or medical condition.
- Disease or medical condition detected or diagnosed after study drug administration even though it may have been present prior to the start of the study.
- Continuous persistent disease or symptoms present at baseline that worsen following the start of the study.
- Lack of efficacy in the acute treatment of a life-threatening disease.
- Events considered by the investigator to be related to study-mandated procedures.

- Abnormal assessments, e.g., ECG and physical examination findings, must be reported as AEs if they represent a clinically significant finding that was not present at baseline or worsened during the course of the study.
- Laboratory test abnormalities must be reported as AEs if they represent a clinically significant finding, symptomatic or not, which was not present at baseline or worsened during the course of the study or led to dose reduction, interruption or permanent discontinuation of study drug.

Adverse events do not include:

- Pre-planned interventions or occurrence of endpoints specified in the study protocol are not considered AE's, if not defined otherwise (eg.as a result of overdose)
- Medical or surgical procedure, e.g., surgery, endoscopy, tooth extraction, transfusion.
 However, the event leading to the procedure is an AE. If this event is serious, the procedure must be described in the SAE narrative.
- Pre-existing disease or medical condition that does not worsen.
- Situations in which an adverse change did not occur, e.g., hospitalizations for cosmetic elective surgery or for social and/or convenience reasons.
- Overdose of either study drug or concomitant medication without any signs or symptoms. However, overdose must be mentioned in the Study Drug Log.

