11.3 Endpoints analysis

The primary endpoint (outcome of NT 4 weeks after the second vaccination) will be analysed using Fisher's Exact Test. For the seroconversion rates, 95% confidence intervals will be calculated. All subjects with available antibody responses fulfilling the eligibility criteria will be included in the analysis

The secondary endpoints (NT 4 weeks after the third vaccination, ELISA prior to the first vaccination and 4 weeks after the second and third vaccination, cellular immunity, immunoglobulin levels and immune reconstitution) will be analysed using descriptive statistics.

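### The systemic-reaction endpoint has no post-dose window or causality rule, and by the visit text controls are asked about adverse events less often than HSCT patients, with no enquiry after dose 3

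*Combined protocol and SAP*

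**What the plan says.** The synopsis gives the tolerability endpoint as "Number of subjects with systemic reactions after vaccination" and lists safety data among the secondary items to be described. Section 8.5.4.2 (secondary endpoints) has no safety item. In 11.3 the list that opens "The secondary endpoints (NT 4 weeks after the third vaccination, ELISA prior to the first vaccination" ends with immune reconstitution and does not mention safety.

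On timing, sections 8.4 and 9.1.1 describe the product: "These side-effects usually occur within 72 hours after the vaccination, abate within 1-2 days". They name "systemic reactions including fever, fatigue, headache, muscular pain, arthralgia" as the systemic reactions, with a frequency between 1/100 and 1/10. Neither section makes this a counting rule. Section 9.1.2 defines an adverse event as any clinically relevant change "that occurs during the course of the study, whether or not considered related to the study drug", and 7.1.4 puts individual participation at 44-56 weeks.

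On causality, 8.4, 9.1.1 and 9.4 require the investigator to judge every event. Section 9.4 has five classes (unrelated, unlikely, possible, probable, definite). The CRF list in 9.5 has three, without unlikely and probable. The CRF also records the start date and time of each event.

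On enquiry, Visit 5 (8.5.2.6) opens with "The following activities will be performed in HSCT patients only", and the same line stands at Visits 7 and 8 (8.5.2.8, 8.5.2.9). At Visit 6, "The investigator will ask all subjects about any adverse experiences occurring since Visit 5". Table 1 marks adverse events at Visits 1 to 8 with no group limit.

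**The concern.** The endpoint will be read as a comparison of tolerability between HSCT recipients and healthy controls. Two things could distort it.

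The first is definition. Fever, fatigue, headache, muscle pain and joint pain are also symptoms of ordinary illness, and section 5.2 says HSCT patients have a raised risk of infection. With no onset window and no causality class tied to the endpoint, an illness months after a dose can enter or stay out according to the judgement of an investigator who knows the group.

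The second is ascertainment. If one group is asked more often, and only that group is asked after the third dose, the counts can differ even if the vaccine is tolerated equally well. Start dates on the CRF help only with events that somebody asked about.

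**Working it through.** The plan gives no figure for this endpoint, so there is none to reproduce.

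**Step 1. Enquiries about adverse events after Visit 1, by the text of 8.5.2**

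| Visit | HSCT | Controls |
|---|---|---|
| 2, 3, 4 | asked | asked |
| 5 | asked | not in text |
| 6 | asked | asked |
| 7, 8 | asked | not in text |
| Total | 7 | 4 |
| After dose 3 | 2 | 0 |

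Both groups are observed for at least 30 minutes after each dose. If Table 1 governs, the totals are 7 and 7.

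**Step 2. Recall at Visit 6, in nominal days.** Visit 4 is Day 56, Visit 5 Day 84, Visit 6 Day 270-365.
- HSCT: 84 − 56 = 28 days to Visit 5, then 270 − 84 = 186 to 365 − 84 = 281 days.
- Controls: 270 − 56 = 214 to 365 − 56 = 309 days in one step. The question refers to Visit 5, which the text does not give them.

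**Step 3. How much background illness a window would remove.** The documents give no illness rate. Assume λ = 0.5, 1 or 2 systemic illnesses per person-year and no vaccine effect. The chance of at least one in d days is 1 − exp(−λ × d / 365.25). A 7-day window after each of three doses gives d = 21; whole follow-up to Visit 8 gives d = 298 to 393.

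| λ per year | 21 days | 298 to 393 days |
|---|---|---|
| 0.5 | 2.8% | 34-42% |
| 1 | 5.6% | 56-66% |
| 2 | 10.9% | 80-88% |

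The right-hand column assumes that every illness is counted with no causality filter, so it is an upper bound.

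**Step 4. What the missing dose 3 enquiry could cost in controls.** Read the documents' 1% to 10% as a per-dose probability p, with doses independent (both are assumptions), and suppose that every dose 3 reaction in controls goes unrecorded.
- Any reaction over three doses, 1 − (1 − p)³: 3.0% to 27.1%, or 0.8 to 7.0 of 26 subjects.
- Any reaction over two doses, 1 − (1 − p)²: 2.0% to 19.0%, or 0.5 to 4.9 of 26.
- Share of affected controls missed: (0.0297 − 0.0199)/0.0297 = 33% at p = 1%, and (0.271 − 0.190)/0.271 = 30% at p = 10%.

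**The case against.** A reader might infer that the endpoint simply counts a year of HSCT background illness as vaccine reactions. The documents do not support that. The endpoint says reactions, not adverse events, and every event must be judged for causality. The related classes in 9.4 require a reasonable temporal sequence, and an event explained by the subject's clinical state points towards unrelated. A febrile infection months after a dose would probably be set aside.

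That stands, but it does not close the gap. The temporal sequence has no limit in days, no class is tied to the endpoint, the two scales differ, and the judgement is open-label. The clinical-state criterion can also work the other way: the same fever soon after a dose may be excused in an HSCT recipient and attributed in a control. The direction of any bias cannot be fixed from the documents.

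A reader might also put in rates such as 1.0 illness per year for HSCT and 0.3 for controls and conclude that 63% versus 26% would be counted (1 − exp(−1.0) and 1 − exp(−0.3)). Neither rate is in the documents. The group gap is then an input, and the figures ignore the causality filter. They are not an expected result.

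On ascertainment, the restriction at Visits 7 and 8 may be a drafting slip. Table 1 has no group limit, 8.5.4.2 limits only immune reconstitution to HSCT recipients, and 7.1.4 and 7.1.5 describe participation and completion through Visit 8 without separating groups. If controls do attend Visits 7 and 8 but not Visit 5, the count is 7 versus 6 and the dose 3 loss in Step 4 disappears. The visit text still says otherwise, and sites follow visit text. The passages contradict each other and must be reconciled.

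Finally, the longer gap to the first enquiry after dose 1 (28 days, against 7 ± 2 after dose 2) is the same in both groups, so it is not a source of inequality between them.

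**Conclusion.** The point holds in this form: the tolerability endpoint lacks an onset window and a causality rule, is absent from 8.5.4.2 and 11.3, and by the visit text is ascertained unequally (7 enquiries against 4, and none in controls after dose 3). Background illness may be counted as reactions; the documents do not show that it will be.

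Under the assumed 0.5-2 illnesses per person-year, a 7-day window per dose would hold background to 2.8-10.9% of subjects, against an unfiltered ceiling of 34-88%. Under the per-dose reading of 1-10%, controls could lose about 30% of affected subjects, at most about 2 of 26, if the visit text governs and no dose 3 reaction reaches the record by another route.

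The consequence is limited. The endpoint is descriptive, in a pilot of 52 subjects. The primary test and the sample size are unaffected. Still, the between-group tolerability result cannot be interpreted safely as the plan stands, and the change is cheap enough that it should be made.

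**What to change.** - Define the endpoint as systemic events with onset within a fixed window after each dose, the same in both groups, using the start date and time already on the CRF. Seven days is one example: it contains the 72-hour onset in 8.4 and 9.1.1 with some margin. The length is a choice for the sponsor to justify.
- State which symptoms count. Either tie a causality class to the endpoint or report it regardless of causality. Use one causality scale in 9.4 and 9.5.
- Report by dose and by group, and list later events separately as adverse events.
- Reconcile Table 1 with 8.5.2.6, 8.5.2.8 and 8.5.2.9 so that both groups are asked alike, including after dose 3. Word the Visit 6 question as since the last attended visit.
- Add the endpoint to 8.5.4.2 and safety to 11.3, in line with the synopsis.

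The cost is mostly wording. If the visit text governs, controls will also need a brief enquiry after dose 3, because start dates cannot recover events that were never asked about. Late reactions would appear only in the adverse event listing. After dose 1, onset would still be recalled at Day 28, in both groups alike.

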3. LIST OF ABBREVIATIONS

AE = Adverse event

CFSE = carboxyfluroescein diacetate succinimidyl ester

CRF = Case Report Form

ELISA = enzyme-linked immunosorbent assay

FACS = fluorescence activated cell sorting

GCP = Good Clinical Practice

GVHD = graft-versus-host disease

HSCT = blood and marrow transplantation

ICH = International Conference on Harmonization

NIH = National Institute of Health

NT = neutralization test

PBMCs = peripheral blood mononuclear cells

PHA = phytohemagglutinin

TBE = tick-borne encephalitis

9.1.2 DEFINITION OF ADVERSE EVENTS	27
9.2 SERIOUS ADVERSE EVENTS (SAES)	28
9.2.1 HOSPITALIZATION – PROLONGATION OF EXISTING HOSPITALIZATION	29
9.2.2 SAES RELATED TO STUDY-MANDATED PROCEDURES	29
9.2.3 SUSPECTED UNEXPECTED SERIOUS ADVERSE REACTIONS (SUSARS)	29
9.2.4 PREGNANCY	30
9.3 SEVERITY OF ADVERSE EVENTS	30
9.4 RELATIONSHIP TO STUDY DRUG	31
9.5 REPORTING PROCEDURES	32

Nr 2011-002928-41	
9.5.1 REPORTING PROCEDURES FOR SAES	32
9.5.2 REPORTING PROCEDURES FOR SUSARS	33
9.5.3 ANNUAL SAFETY REPORT	34
10. FOLLOW-UP	34
11. STATISTICAL ANALYSIS	34
11.1 SAMPLE SIZE CONSIDERATIONS	34
11.2 RELEVANT PROTOCOL DEVIATIONS	35
11.3 ENDPOINTS ANALYSIS	35
11.4 MISSING, UNUSED AND SPURIOUS DATA	35
11.5 INTERIM ANALYSIS	35
11.6 SOFTWARE PROGRAM(S)	35
12. DOCUMENTATION AND DATA MANAGEMENT	35
12.1 DOCUMENTATION OF STUDY RESULTS	35
12.1.1 CASE REPORT FORM (CRF)	36
12.1.2 DATA COLLECTION	36
12.2 SAFEKEEPING	36
12.3 QUALITY CONTROL AND QUALITY ASSURANCE	37
12.3.1 PERIODIC MONITORING	37
12.3.2 AUDIT AND INSPECTIONS	38
12.4 REPORTING AND PUBLICATION	38
12.4.1 PUBLICATION OF STUDY RESULTS	38
13. ETHICAL AND LEGAL ASPECTS	38
13.1 INFORMED CONSENT OF SUBJECTS	38
13.2 ACKNOWLEDGEMENT / APPROVAL OF THE STUDY	39
13.2.1 CHANGES IN THE CONDUCT OF THE STUDY	39
13.3 INSURANCE	40
13.4 CONFIDENTIALITY	40
13.5 ETHICS AND GOOD CLINICAL PRACTICE (GCP)	40
14. APPENDICES	41
15. REFERENCES	42

TABLE 1. VISIT AND ASSESSMENT SCHEDULE

PERIODS	Name	SCREENING	VACCINATION 44-56 weeks							
	Duration									
VISITS	Number	1	2	3	4	5	6	7	8	9
	Name	Screening	Visit 1/ 1 st Vaccination	Visit 2/ 2 nd Vaccination	Visit 3	Visit 4	Visit 5	Visit 6/ 3 rd Vaccination	Visit 7	Visit 8
	Time	Day – 28	Day 0	Day 28 (± 2 days)	Day 35 (7 ± 2 days after Visit 2)	Day 56 (28 ± 7 days after Visit 2)	Day 84 (± 14 days)	Day 270- 365	Day 277-372 (7± 2 days after Visit 6)	Day 298-393 (28 ± 7 days after Visit 6)
Informed Consent X		Х								
Inclusion / Exclus	ion Criteria	Х	Х							
Medical History		Х	Х							
Physical Examina	tion	Х	Х	Х				Х		
Pregnancy Test		Х	Х	Х		Х	Х	Х		Х
Blood Draw (Sero	logy)	Х				Х				Х
Blood Draw (Cellular immunity)		Х			Х				Х	
Blood Draw (Imm reconstitution + s immunoglobulin	erum	х					х	х		
Vaccination			Х	Х				Х		
Adverse Events			Х	Х	Х	Х	Х	Х	Х	Х

